21.0 Process to Document Consent in Writing

Participants will complete the Informed Consent document.

22.0 HIPAA

Study will be performed in compliance with HIPAA regulations. A partial waiver is requested for study recruitment. Subjects will be asked to sign a HIPAA authorization to allow access to their private information.

23.0 Data Management

Data will be stored in a study paper file at BostonSight. Electronic data will be stored on a password-protected computer in a locked office. All study data will remain at BostonSight for a minimum of 3 years following study completion. The principal investigator will be responsible for maintaining study data security and subject confidentiality, and the PI and the study coordinator will be responsible for receipt and transmission of the data. The investigative team and inspectors from regulatory agencies such as the US Food and Drug Administration will have access to the data if requested for study monitoring or an audit.

All collected data will be documented on study documents and analyzed for differences between baseline and test data. Hypothesis testing will be performed using statistical analyses including parametric or nonparametric comparisons (i.e., t-tests, signed-rank tests), analysis of variance, general linear models, correlation, or regression techniques.

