1.0 Objectives

The goal of this pilot study is to determine the precision and accuracy of measurements of intraocular pressure (IOP) when a PROSE (Prosthetic Replacement of the Ocular Surface Ecosystem) scleral lens is on the eye.

The PROSE device (PD) is a specialized scleral lens that is filled with preservative-free saline and then applied to the eye in order to treat a variety of ocular conditions. The PROSE device vaults the cornea without touch and lands gently on the conjunctival tissue overlying the sclera. Because scleral lenses vault and therefore cover the cornea, measuring IOP during lens wear is challenging as traditional techniques rely on corneal contact. Measuring IOP before insertion and after removal of the PROSE device likely does not correspond to the IOP when the lens is actively on the eye.

This is a prospective study of the precision and accuracy of tonometry measurements with scleral lens wear. Three non-traditional means of IOP measurements will be used: scleral TonoPen, scleral pneumatonometry, and transpalpebral Diaton tonometer. Data on precision and accuracy of these instruments in this pilot study aims to guide decision making in a full study on the effects of scleral lenses on IOP.

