9.0 Study Endpoints

The study design allows for the subjects to serve as their own control. The subjects' baseline IOP will be measured with the standard clinical approach via corneal TonoPen. Corneal TonoPen was chosen as the control method for intraocular pressure measurements as it is a standard of care method and process used every day in clinical practice by ophthalmologists and optometrists. This will be compared to the IOP measurement obtained in the same subject with lenses in place.

The primary endpoints in this study are as follows:

- 1. Intraocular pressure
 - a. TonoPen, corneal without lens
 - i. Baseline, one measurement
 - b. TonoPen, scleral with lens
 - i. IOP and confidence level will be recorded
 - ii. Attempt 5 measurements maximum
 - Goal of achieving 3 measurements in total with confidence level of 90% of higher
 - iii. One measurement defined as a completed result or attempting to measure until the machine times out
 - c. Pneumatonometer, scleral with lens
 - i. Measurement in "manual IOP mode"
 - ii. IOP and standard deviation (SD) will be recorded for each measurement
 - iii. Attempt 10 measurements maximum
 - Goal of achieving 3 measurements in total with a SD of 2 mmHg or less
 - iv. One measurement defined as a completed result or attempting to measure until the machines times out
 - d. Diaton, transpalpebral with lens

- i. Up to 6 individual attempts are included in each complete measurement, with the instrument averaging the measurements for a result
- ii. Reliable average is confirmed:
 - When the instrument shows symbol <> and the mean IOP value is non-flickering
 - When the instrument shows symbol <> and the mean IOP value is flickering with a result of equal or less than 19 mmHg
- iii. Attempt 5 complete measurements maximum
 - Goal of achieving 3 reliable measurements
 - Reliability defined (per manufacturer Diaton, Ryazan State Instrument-Making Enterprise, www.diaton-tonometer.com) as:
 - a. +/- 2mmHg error in range 5-20mmHg
 - b. +/- 10% error in range 20-60mmHg

Correct calibration of each instrument will be ensured prior to the study per individual manufacturer's standards. The first measurement of every subject will not be included but will serve as one practice measurement to familiarize the subject with the measurement process.

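### The goal is precision and accuracy, but the only analysis described is testing of baseline-versus-test differences, with no repeatability or agreement estimate

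*Protocol*

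**What the plan says.** **Goal.** Protocol Section 1.0 sets out to "determine the precision and accuracy of measurements of intraocular pressure (IOP") with the scleral lens in place. The result "aims to guide decision making in a full study on the effects of scleral lenses on IOP". The same section says that pressure measured with the lens off "likely does not correspond to the IOP when the lens is actively on the eye".

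**Data.** Under Section 9.0 the reference is corneal TonoPen without the lens: "Baseline, one measurement". Each lens-on instrument is read repeatedly:
- Scleral TonoPen: up to 5 attempts, aiming for 3 readings at 90% confidence or better.
- Pneumatonometer: up to 10 attempts, "Goal of achieving 3 measurements in total with a SD of 2 mmHg or less".
- Diaton: up to 5 complete measurements, aiming for 3 reliable ones.

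Each subject's first reading is practice and is dropped. Section 9.0 also says that baseline will be compared with the lens-on value in the same subject. Section 10.0 has both eyes measured, and Section 5.0 puts 10 subjects in each instrument cohort.

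**Analysis.** The only analysis text is in Section 23.0. Data will be "analyzed for differences between baseline and test data", and "Hypothesis testing will be performed using statistical analyses including parametric or nonparametric comparisons (i.e., t-tests, signed-rank tests), analysis of variance"; the list ends with "analysis of variance, general linear models, correlation, or regression techniques".

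**The concern.** Precision is the spread of repeat readings on the same eye. Accuracy, for an individual reading, depends on both the mean bias and the scatter of errors around it. A test of the baseline-versus-test difference addresses only whether the mean bias is zero. It says nothing direct about repeatability and does not report the scatter. Correlation, also listed, ignores a constant bias. The SD, confidence and reliability rules in Section 9.0 decide whether a single reading is accepted; they are not study-level estimates of precision.

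The pilot exists to inform a full study. That study needs, for each instrument, a within-eye SD (for sample size and the number of readings) and an interval for individual disagreement (for choosing an instrument). Section 23.0 can be carried out to the letter without producing either. With 10 subjects per instrument, a non-significant difference could then be read as agreement. The protocol does not say that it will be, but it offers no other criterion.

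**Working it through.** **1. The protocol's own figure.** The only derived number is about 33 recruits for 30 completers with 10% drop-out: 30 × 1.10 = 33, or 30/0.90 = 33.3, rounded up to 34. It reproduces closely and has no bearing on this point. There is no power or precision calculation to reproduce.

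**2. Objective against analysis.**

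| Part of the goal | Data collected (9.0, 10.0) | Served by the target in 23.0? |
|---|---|---|
| Precision | Repeat lens-on readings, both eyes | No |
| Accuracy: mean bias | Lens-on reading against one baseline reading | In part, as a test |
| Accuracy: scatter of individual errors | Same | No |

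**3. Inputs.** From the protocol: n = 10 per instrument, two eyes, a goal of 3 readings, and 2 mmHg as a yardstick. The 2 mmHg is the manufacturer's error figure for the Diaton at 5–20 mmHg (Section 9.0), borrowed here for all three instruments. Assumed, because the protocol gives none: SD of lens-on minus baseline differences of 2, 3 and 4 mmHg, two-sided alpha of 0.05, and normal errors.

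**4. The test does not respond to precision.** In 100,000 simulated trials per setting (zero bias, n = 10, mean of 3 readings, baseline SD 1.5 mmHg assumed), a paired t-test rejected in 5.0%, 5.0%, 4.9% and 5.0% of trials at within-subject SDs of 1, 2, 4 and 6 mmHg. At zero bias, the share of single differences beyond 2 mmHg is 2 × [1 − Φ(2/SD)].

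**5. Non-significance is weak evidence of accuracy.** Power comes from the noncentral t distribution with 9 df and noncentrality (2/SD) × √10. For the mean of two eyes, SD is replaced by SD × √((1 + r)/2), with between-eye correlation r from 0.9 to 0.3.

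| SD of differences (mmHg) | Differences beyond 2 mmHg at zero bias | Power for 2 mmHg bias, one value per subject | Power, mean of two eyes |
|---|---|---|---|
| 2 | 32% | 80% | 82–94% |
| 3 | 50% | 47% | 49–65% |
| 4 | 62% | 29% | 31–42% |

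The noisier the instrument, the more often a real 2 mmHg bias goes undetected.

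**6. What the planned data could deliver instead.**
- *Within-eye SD.* 10 subjects × 2 eyes × (3 − 1) = 40 df. The 95% limits are √(df/χ²) at the 97.5% and 2.5% points, or 0.82 to 1.28 times the estimate. If the dropped practice reading leaves 2 readings per eye, df = 20 and the limits are 0.77 to 1.44 times.
- *Repeatability coefficient.* 1.96 × √2 × within-eye SD = 2.77 × SD. An SD of 2 mmHg would give 5.5 mmHg.
- *Limits of agreement.* Bias ± 1.96 SD, so ± 3.9, 5.9 and 7.8 mmHg at SD 2, 3 and 4. With one value per subject, the 95% CI half-width of each limit is 2.262 × √(3/10) = 1.24 SD, or 2.262 × √(1/10 + 1.96²/18) = 1.27 SD. With two eyes modelled, simulation (40,000 runs, r = 0.3 to 0.9) gives 0.95 to 1.20 SD.

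**The case against.** The choice of estimator is normally left to the SAP, which is not shown. Section 23.0 is a short summary with an open list, and it excludes nothing. A paired comparison yields the mean bias, and an analysis of variance of the repeats yields a within-eye variance, so the plan could be followed while producing both. The harm from misreading a non-significant test is inferred, since no decision rule is stated. The SDs are assumed, and the 2 mmHg belongs to one instrument and part of its range. The power figures concern a test of means, not the missing precision estimate.

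Much of this is fair, and it sets limits. Mean bias is partly covered, the power figures are illustrative, and the absence of a named statistic would not by itself be a finding. What stands is the mismatch. The protocol does state an analysis target, and that target is not repeatability or scatter, although precision is a stated goal and repeat readings are collected for it. No other section fills the gap. An SAP could add the estimates, but the protocol sentence would still describe a different purpose.

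**Conclusion.** The concern holds. Section 23.0 sets an analysis that does not answer the objective in Section 1.0: precision is not addressed, and accuracy is addressed only through a test of the mean difference. The mismatch itself rests on the text and needs no assumed figure. Its illustrated size does rest on assumptions. With SDs of differences of 2 to 4 mmHg, between 32% and 62% of single differences exceed 2 mmHg in an instrument with no mean bias, and a true 2 mmHg bias is detected with 80% down to 29% power. The data to do better are already planned, so this should be corrected, but it does not invalidate the study.

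**What to change.** Replace the hypothesis-testing sentence in Section 23.0 with estimation for each instrument:

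- **Precision.** Within-eye SD and repeatability coefficient (2.77 × SD) with 95% CIs, from a model with random effects for subject and for eye within subject. Exclude the practice reading. Report once for all completed readings and once for those meeting the Section 9.0 cut-offs, because the accepted readings alone may flatter precision.
- **Agreement with lens-off corneal TonoPen.** Mean difference with 95% CI, and 95% limits of agreement with CIs, allowing for two eyes per subject and read against a tolerance fixed before analysis.
- **Labelling.** Describe the agreement result as instrument error plus error in the single baseline reading plus any lens effect on pressure, not as pure accuracy. Section 1.0 itself says that lens-off and lens-on pressure likely differ.
- **Interpretation.** State that a non-significant test or a correlation is not evidence of accuracy.

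**Cost.** No extra subjects or measurements. Readings that miss the cut-offs must be kept. Section 9.0 already records the value with its confidence level or SD for TonoPen and pneumatonometer; the Diaton needs a reliable/not-reliable field. A tolerance must be agreed. The limits of agreement will be imprecise, each known only to about ±1.2 to 1.3 SD with one value per subject, or ±0.95 to 1.2 SD with both eyes modelled. No analysis of these data can separate instrument accuracy from a lens effect.

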5.0 Number of Subjects

A minimum of 30 subjects will be enrolled in this study with 10 subjects in each of the three cohorts. This is a low risk study. We can expect an approximate 10% drop-out rate, so we will expect to recruit approximately 33 subjects; and the first 30 to be eligible and complete the study will be used for data analysis.

The first 10 subjects that are eligible to proceed and consented will be consecutively enrolled in the first cohort (scleral TonoPen). The second 10 subjects that are eligible to proceed and consented will be consecutively enrolled in the second cohort (scleral pneumatonometry). The third 10 subjects that are eligible to proceed and consented will be consecutively enrolled in the third cohort (Diaton). Sequential assignment allows for focus on one instrument and one technique at a time by one investigator.

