10.0 Procedures Involved

Once a subject has been identified, the initial visit will be scheduled.

During the visit:

- 1. Informed consent will be completed
- 2. Record the patient's general medical history and habitual contact lens information, including lens design, power, and diameter.
- 3. An investigator will conduct visual acuity assessments of both eyes (Snellen).
- 4. Assess the fit of the PROSE device via slit lamp assessment of both eyes.
- 5. Assess the cornea and conjunctiva of both eyes with the PROSE device on and off.
- 6. Measure corneal intraocular pressure of both eyes after PROSE device removal
- 7. The investigator will instill one drop of topical anesthetic in both eyes followed by a lubricating preservative-free artificial tear drop, such as Refresh Plus, prior to IOP measurements.
- 8. Measure intraocular pressure of both eyes with the PD on via (method depends on which cohort the subject is in):
 - a. Scleral TonoPen
 - b. Scleral pneumatonometry
 - c. Transpalpebral Diaton
- 9. Reassess the ocular surface of both eyes after intraocular pressure measurement at the slit lamp biomicroscope with and without fluorescein staining in order to rule out adverse events, such as conjunctival abrasion or erosion or other irritations.

Procedure	Length of Time	Frequency of Repetition
	Required for	

Informed consent & HIPAA	20 minutes	Once
General History and Medications	10 minutes	Once
Visual Acuity	2 minutes	Once
Slit-lamp Examination (with PD)	4 minutes	Once
Corneal IOP Measurement (TonoPen)	5 minutes	Once
IOP Measurement (One of the below will be completed)		
COHORT 1: Scleral TonoPen		5 (maximum)
COHORT 2: Scleral Pneumatonometer	20 minutes	10 (maximum)
COHORT 3: Transpalpebral Diaton		5 (maximum)
Slit-lamp Examination after measurement	4 minutes	Once
TOTAL TIME	65 minutes	

The testing descriptions are summarized in the table below:

Test	Description
General History	Participants will be asked questions about their general, ocular and
and Medications	medication use histories along with contact lens use history if applicable.
Lens Evaluation	The PROSE device fit and vision will be evaluated.
Visual Acuity	The participant's vision in each eye while wearing lenses will be measured with a high contrast visual acuity chart. The participant will be asked to cover one eye and read the chart, and this procedure will be repeated for the other eye.
Slit-lamp	The participant's front portion of each eye and contact lenses will be

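### Section 23 commits the accuracy aim to tests of zero difference or zero association with 10 subjects per tonometer; as specified, none of these can show agreement with the corneal reading

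*Protocol*

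**What the plan says.** Protocol Section 1.0 sets the goal: to "determine the precision and accuracy of measurements of intraocular pressure (IOP) when a PROSE" scleral lens is worn. It also says what the results are for: "Data on precision and accuracy of these instruments in this pilot study aims to guide decision making in a full study". Section 9.0 makes the corneal TonoPen reading, taken without the lens, the control, and says "This will be compared to the IOP measurement obtained in the same subject with lenses in place".

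Section 5.0 fixes the size: "A minimum of 30 subjects will be enrolled in this study with 10 subjects in each of the three cohorts". Each cohort uses one tonometer, so each instrument is judged on 10 subjects. Section 10.0 has both eyes measured.

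Section 23.0 sets the mode of analysis: "All collected data will be documented on study documents and analyzed for differences between baseline and test data". The next sentence begins "Hypothesis testing will be performed using statistical analyses including parametric or nonparametric comparisons (i.e., t-tests, signed-rank tests" and continues with ANOVA, general linear models, correlation and regression. It states no significance level, no accuracy margin and no rule for choosing an instrument.

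Section 9.0 does contain two tolerances: the manufacturer's error band for the Diaton (2 mmHg either way below 20 mmHg, 10% above) and the pneumatonometer goal of an SD of at most 2 mmHg. Both define an acceptable reading. Neither is a criterion for agreement with the corneal reading.

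**The concern.** When accuracy is the question, the favourable answer is a small difference from the reference, known with adequate precision. A t-test or signed-rank test takes zero difference as its null. It can produce evidence against agreement but none for it. A non-significant result from 10 subjects fits both a negligible bias and a large one.

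The pilot is meant to inform the design of a full study. If its report gives p-values, the natural shorthand is that an instrument not significantly different from corneal TonoPen performed well. That shorthand passes many biased instruments. At a given bias in mmHg, it passes a noisy instrument more readily than a steady one.

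**Working it through.** **The plan's own figure.** The protocol gives no power, alpha or effect size. Its only sample-size arithmetic is the recruitment number: "We can expect an approximate 10% drop-out rate, so we will expect to recruit approximately 33 subjects". Adding 10% to 30 gives 30 × 1.10 = 33; dividing by the completion rate gives 30 / 0.90 = 33.3. The stated figure is consistent with both and is not at issue.

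**Inputs.** From the protocol: n = 10 per tonometer, a within-subject comparison, two eyes measured. Assumed, because the protocol does not state them: two-sided alpha 0.05, normally distributed differences, and a range of SDs for the differences.

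**What each listed method tests.**
- *t-test and signed-rank test:* zero mean or median difference.
- *ANOVA across cohorts:* equal means between instruments. A bias shared by all three leaves this null true. With 3 × 10 subjects and one value each, a 1-SD shift in one instrument is missed 42% of the time (noncentral F, 2 and 27 degrees of freedom).
- *Correlation:* zero association. Since corr(X, Y + c) = corr(X, Y), no constant bias affects it.
- *Regression and general linear models:* testing a zero slope is again a test of association. Testing slope 1 and intercept 0 would make failure to reject the favourable result. These models can yield an estimated bias with an interval, but Section 23 does not make that the basis of the assessment.

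**Miss rate at a bias of 0.5 SD, one value per subject.** Degrees of freedom 9, critical value t = 2.262, noncentrality = 0.5 × √10 = 1.58. Power is P(|T| > 2.262) under the noncentral t, which is 0.293. The miss rate is 1 − 0.293 = 0.707. By simulation, the signed-rank test misses about 72%.

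**Two eyes averaged per subject.** With inter-eye correlation ρ of the differences, the SD of the subject mean is SD × √((1 + ρ)/2), so the standardised bias is 0.5 / √((1 + ρ)/2).

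| ρ | standardised bias | miss rate |
|---|---|---|
| 0 | 0.707 | 49% |
| 0.5 | 0.577 | 63% |
| 0.8 | 0.527 | 68% |
| 1 | 0.500 | 71% |

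**Fixed bias of 2 mmHg, one value per subject.** The standardised bias is 2 / SD.

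| assumed SD of differences (mmHg) | 2 / SD | miss rate |
|---|---|---|
| 2 | 1.00 | 20% |
| 3 | 0.67 | 53% |
| 4 | 0.50 | 71% |
| 6 | 0.33 | 84% |

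The test reaches 80% power only at a bias of about 1.0 SD. For 0.5 SD it would need 34 subjects per tonometer.

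**What estimation gives from the same data.**
- The 95% interval for the mean difference has half-width 2.262 × SD / √10 = 0.72 SD, which is 1.4, 2.1, 2.9 and 4.3 mmHg at SDs of 2, 3, 4 and 6 mmHg.
- Each 95% limit of agreement has an approximate interval half-width of 2.262 × SD × √(1/10 + 1.96²/18) = 1.27 SD, which is 2.5, 3.8, 5.1 and 7.6 mmHg.

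**The case against.** - **No decision rule exists.** Section 23 nowhere equates non-significance with accuracy. A reader might infer that 'no significant difference' is the only favourable result open to an instrument. The text does not support that: the list is open-ended, it includes regression and general linear models, and a paired t-test also yields an estimated difference with an interval. This stands, so the miss rates describe a reading of the results and not a stated rule.
- **An analysis plan may exist.** Limits of agreement and margins are often left to it, so their absence alone is no finding. What remains is that the protocol itself chooses hypothesis testing for an accuracy aim.
- **The 71% is an upper figure.** It assumes one value per subject. Averaging two eyes gives 49% to 71%. This stands.
- **Noise may count elsewhere.** A reader might infer that the plan favours the noisiest instrument and that the worse one would go forward. That is too strong. At a bias fixed in SD units, every instrument has the same miss rate; the gradient appears only at a bias fixed in mmHg. It concerns the accuracy verdict alone, while precision is a separate aim with its own reading-quality records in Section 9.0.
- **Zero may not be the right target.** Section 1.0 itself says that lens-off pressure likely does not match lens-on pressure, so an accurate tonometer could show a real non-zero difference. This stands and argues against a compulsory pass/fail margin around zero. It equally undermines a test of zero difference.

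**Conclusion.** The point holds in a limited form. Section 23 answers an agreement question with tests of zero difference or zero association on 10 subjects per tonometer, and as specified none of them can demonstrate agreement with the corneal reading.

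The size is conditional on a non-significant result being read as accuracy. In that case the difference test would overlook a 0.5-SD bias roughly half to seven-tenths of the time, and would overlook a fixed mmHg bias more often as scatter rises. These figures rest on the assumed alpha, normality and SDs. The mismatch between question and method does not depend on them.

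The protocol does not state that reading, and it does not say that the instrument for the full study will be chosen by p-value.

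**What to change.** In Section 23.0, make the following the basis of the accuracy assessment for each tonometer: the mean difference from corneal TonoPen with its 95% confidence interval, and the 95% limits of agreement with their confidence intervals. Compute these at subject level or with a method that allows for two eyes per subject. Keep any p-values descriptive. Add a sentence such as: *A non-significant difference or a significant correlation will not be taken as evidence of accuracy.*

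If the sponsor wishes to label an instrument as agreeing with the reference, set a margin in mmHg beforehand, require the whole interval to lie inside it, and acknowledge that the difference also contains any true effect of the lens on pressure.

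The cost is wording, plus one margin if labels are used. No extra subjects or procedures are needed. The downside is candour about small numbers. Taking a margin of 3 mmHg purely as an illustration, with zero true bias and one value per subject, the 95% interval would lie inside it in about 97%, 61% and 23% of trials at SDs of 2, 3 and 4 mmHg. Some instruments will therefore be reported as inconclusive.
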